7.2.3 Efficacy

7.2.3.1 Attention-deficit/Hyperactivity Rating Scale

The ADHD-RS-5 Child, Home Version (DuPaul et al. 2016), the primary efficacy measure, is completed by the clinician and will be administered at baseline (Visit 2) and each subsequent visit up to and including Visit 6/ET to capture the ADHD symptoms within each study period.

The ADHD rating scale was developed to measure the behaviors of children with ADHD and is commonly used in clinical studies of ADHD (Buitelaar et al. 2007; Döpfner et al. 2006; Kratochvil et al. 2001; Michelson et al. 2001; Spencer et al. 2001). The ADHD-RS-5 consists of 18 items designed to reflect current symptomatology of ADHD based on DSM-5 criteria. Each item is scored on a 4-point scale ranging from 0 (reflecting no symptoms) to 3 (reflecting severe symptoms) with total scores ranging from 0-54. The 18 items may be grouped into 2 subscales: hyperactivity/impulsivity (9 items) and inattentiveness (9 items).

The ADHD-RS-5 should be completed by a clinician experienced in the evaluation of children with ADHD. Since the ADHD-RS-5 is an important measure for guidance in dosing decisions, the ADHD-RS-5 must be performed by an individual who is experienced with the scale. All individuals performing this assessment must be pre-approved by the sponsor or designee.

The title, version, and date of the ADHD-RS-5 used in this study are included in Appendix 3.

7.2.3.2 Clinical Global Impression

The Clinical Global Impression Scale (Guy 1976) permits a global evaluation of the subject's severity and improvement over time. The Clinical Global Impression has been used extensively in clinical studies of ADHD (Michelson et al. 2001; Weiss et al. 2005; Wilens et al. 2001).

The investigator will perform the CGI-S to rate the severity of a subject's condition on a 7-point scale ranging from 1 (normal, not at all ill) to 7 (among the most extremely ill subjects) at the baseline visit (Visit 2). Additionally at the baseline visit, the investigator should establish 3 target areas of improvement with the subject and the subject's parent/LAR.

To generate the targets, an open-ended question such as "If this program of treatment works for

your child, what things do you hope he/she will be doing better?" should be asked. Ratings will be completed with respect to ADHD symptoms.

At each visit from Visit 3 up to and including Visit 6/ET, the investigator will assess the subject's improvement relative to the 3 target areas of improvement recorded at the baseline visit (Visit 2), on the CGI-I, a 7-point scale ranging from 1 (very much improved) to 7 (very much worse).

The CGI-S and CGI-I should be completed by a clinician experienced in the evaluation of children with ADHD. Since the CGI-I is an important measure for guidance in dosing decisions, the CGI-I must be performed by a principal investigator or sub-investigator who is medically/clinically responsible for the subject and experienced with the scale. All individuals performing this assessment must be pre-approved by the sponsor or designee.

The title, version, and date of the CGI-S and the CGI-I used in this study are included in Appendix 3.

7.2.4 Safety

The name and address of each third party vendor (eg, clinical laboratory) used in this study will be maintained in the investigator's and sponsor's files.

7.2.4.1 Medical and Medication History

The investigator will perform a complete medical history at the screening visit (Visit 1), including a medication history, and record all information gathered. The investigator must record all clinically or medically relevant information regardless of how much time has elapsed since the date of diagnosis.

With the subject and parent/LAR consent, medical records from other treatment providers should be requested.

7.2.4.2 Physical Examination

A full physical examination will be performed at the screening visit (Visit 1) and Visit 6/ET. Additionally, an abbreviated physical examination is required at the baseline visit (Visit 2) if more than 32 days have elapsed since the physical examination completed as part of the screening visit (Visit 1) was performed. The physical examination will be performed by a qualified, licensed individual per local requirements (eg, physician, physician assistant, or nurse practitioner).

A full physical examination is composed of a review of the following body systems:

- General appearance
- Skin
- Head, Eyes, Ears, Nose, and Throat

Page 48

- Spine/Neck/Thyroid
- Respiratory
- Cardiovascular
- Abdomen (including liver and kidneys)
- Musculoskeletal
- Neurological

If an abbreviated physical examination is required at the baseline visit (Visit 2), a review of the body systems will include the following:

- General Appearance
- Respiratory
- Cardiovascular

Abnormalities identified at the screening visit (Visit 1) will be documented in the subject's source documents. Changes after the screening visit (Visit 1) will be captured as AEs, as determined by the investigator.

7.2.4.3 Adverse Event Collection

At each study visit, parent/LAR and/or subject will be questioned in a general way to ascertain if AEs have occurred since the previous visit (eg, "Have you had any health problems since your last visit?"). Adverse events are collected from the time informed consent is signed. (Refer to Section 8.) This information should be collected prior to the completion of assessments at all study visits. In addition, any symptoms/conditions reported during assessments and deemed to be clinically significant by the investigator will be assessed as AEs.

7.2.4.4 Vital Signs (Including Height and Weight)

Measurements of oral or tympanic temperature and sitting respiratory rate will be performed at the screening visit (Visit 1) and/or baseline (Visit 2) only.

Measurements of sitting systolic and diastolic blood pressure and pulse will be performed at each visit to the site. Blood pressure, pulse, and respiratory rate will be determined after subjects have remained seated for a minimum of 3 minutes.

Blood pressure will be determined by an age-appropriate cuff (the same unit and same arm should be used throughout the study). A blood pressure cuff appropriate for the subject's arm length and girth should be used for all blood pressure measurements. The age-appropriate cuff should be approximately two-thirds the length/width of the subject's arm (from elbow to shoulder). All blood pressure measurements should be taken using the same arm and be performed by the same site personnel (if possible) throughout the study.

The age-appropriate cuff will obtain 3 measurements with approximately 2 minutes in between each collection for blood pressure and pulse and report the average of the 3 measurements for

each parameter. The 3 individual measurements, time collected, and averaged reading should be recorded in the source.

Height will be captured at the screening visit (Visit 1). A calibrated stadiometer must be used for all height measurements. Height should be measured in inches or centimeters without shoes with the subject standing on a flat surface and with chin parallel to the floor. The body should be straight but not rigid.

Weight will be captured at each visit to the site. The same calibrated scale should be used for all weight measurements. Weight should be measured in pounds or kilograms without shoes and with light clothing and should be recorded to the nearest 0.1 pound or 0.1 kilogram.

Any clinically significant deviations from screening (Visit 1) vital signs which are deemed clinically significant in the opinion of the investigator are to be recorded as an AE.

7.2.4.5 Clinical Laboratory Evaluations

All clinical laboratory assays will be performed according to the laboratory's normal procedures. Reference ranges are to be supplied by the laboratory and will be used to assess the clinical laboratory data for clinical significance and out-of-range pathological changes. The investigator should assess out-of-range clinical laboratory values for clinical significance, indicating if the value(s) is/are not clinically significant or clinically significant. Abnormal clinical laboratory values, which are unexpected or not explained by the subject's clinical condition, may, at the discretion of the investigator or sponsor, be repeated as soon as possible until confirmed, explained, or resolved.

Clinical laboratory assessments will be performed at the screening visit (Visit 1) and Visit 6/ET. Additionally, clinical laboratory tests are required to be repeated prior to the baseline visit (Visit 2) with results reviewed before enrolling the subject in the study if more than 32 days have elapsed since the clinical laboratory assessments completed as part of the screening visit (Visit 1) were performed.

The following clinical laboratory assessments will be performed:

Biochemistry and Endocrinology

A blood sample (~5 mL) for biochemistry will be taken to assess the following parameters:

Total Cholesterol Calcium

Aspartate Aminotransferase Urate

Phosphorus Blood Urea Nitrogen

Alanine Aminotransferase Total Bilirubin

Shire CONFIDENTIAL Page 50

Study Protocol SHP465-309

P465-309 07 September 2017

Sodium Creatinine

Alkaline Phosphatase Glucose

Potassium Albumin

Gamma Glutamyl Transferase Protein

Thyrotropin Lactate Dehydrogenase

Thyroxine, Free

Hematology

A blood sample (~4 mL) for hematology will be taken to assess the following parameters:

Hemoglobin Neutrophils

Hematocrit Lymphocytes

Red Blood Cells Monocytes

Platelets Eosinophils

White Blood Cell count – total and

Mean Corpuscular Hemoglobin

differential

Neutrophils Band Form

Basophils

Mean Corpuscular Hemoglobin Concentration Mean Corpuscular Volume

Urinalysis

A urine sample (~10 mL) for urinalysis will be collected to assess the following parameters:

Glucose pH

Specific Gravity Urobilinogen

Blood

Ketones Leukocyte Esterase

Protein Nitrite

Bilirubin

If urinalysis detects protein and/or blood, a microscopic examination will be conducted. The microscopic examination will consist of red blood cells, white blood cells, casts, and bacteria.

7.2.4.6 Urine Drug Screen

A urine drug and alcohol screen will be conducted at the screening visit (Visit 1). As a reminder, a urine drug screen should be repeated prior to the baseline visit (Visit 2) if more than 32 days have elapsed since the screening visit (Visit 1).

Urine samples (~10 mL) will be collected for this testing and will be evaluated at the central laboratory. The following drugs/drug classes will be tested:

Urine Drug Screen

CocaineCannabinoidsPhencyclidined-amphetamineBenzodiazepines classBarbiturates classOpiates classPropoxypheneMethaqualoneMethadone

Methamphetamine

The urine drug screen must be negative at the screening visit (Visit 1) for the subject to be eligible to enroll in the study.

If the subject has a positive urine drug screen at the screening visit (Visit 1) that the investigator is able to attribute to a medication that has been prescribed to the subject, the urine drug screen must be repeated prior to the baseline visit (Visit 2) and must be negative so the investigator can verify that the disallowed medication which caused a positive result at the screening visit (Visit 1) has been discontinued prior to the baseline visit (Visit 2).

7.2.4.7 Pregnancy Test

A serum β -HCG pregnancy test is performed on all females of child-bearing potential at the screening visit (Visit 1). Additionally, the serum pregnancy test must be repeated at the baseline visit (Visit 2) if greater than 32 days have elapsed since the screening visit (Visit 1). The results must be reviewed by the investigator before the subject can be randomized.

A urine pregnancy test is performed on all females of child-bearing potential at the baseline visit (Visit 2), and at the final visit (Visit 6/ET), or if pregnancy is suspected, or on withdrawal of the subject from the study.

7.2.4.8 Electrocardiogram

A 12-lead ECG will be performed at the screening visit (Visit 1), Visit 4, and Visit 6/ET. At screening, 3 ECGs taken approximately 3 minutes apart will be collected; if >32 days have passed since screening, these ECGS will be collected in triplicate at Visit (Visit 2) to ensure appropriate baseline intervals are established. Additional ECGs may be performed during the study at the investigator's discretion.

Page 52

07 September 2017

All ECGs will be performed after 3 minutes of rest using the central ECG provider's equipment and will be sent to the central ECG provider electronically.

The initial interpretation of the ECG, normal or abnormal and clinical significance, will be performed immediately after collection to ensure the safety of each subject. An ECG tracing will then be evaluated by a cardiologist at a central ECG reading vendor and returned to the site with a determination of normal or abnormal. Upon review of the report from this vendor, the investigator will re-evaluate the clinical significance of the ECG while taking into consideration all other safety data available for the subject.

Although a central ECG reader is being used for this study, the eligibility of the subject is based on the investigator's assessment of the ECG. If abnormal and significant results are observed following assessment by the central reader, the investigator, in consultation with the appointed CRO medical monitor, reconfirms subject eligibility to continue.

All ECGs transmitted to the central ECG reader will be analyzed. If the central ECG reader receives multiple ECGs, the first readable ECGs will be analyzed as the scheduled ECG. Every ECG transmitted to the central ECG reader will have corresponding source document data collected. No ECG should be deleted by study site personnel. All ECGs must be transmitted to the central provider regardless of quality, results, or number of ECGs taken at a respective visit.

7.2.4.9 Children's Sleep Habits Questionnaire

The CSHQ is a tool designed to screen for the most common sleep problems in children and consists of 33 items for scoring and several extra items intended to provide administrators with other potentially useful information about respondents. The instrument evaluates the child's sleep based on behavior within 8 different subscales: bedtime resistance, sleep onset delay, sleep duration, sleep anxiety, night wakings, parasomnias, sleep disordered breathing, and daytime sleepiness. The CSHQ will be conducted at each visit to the site starting with the baseline visit (Visit 2) and will be completed by the subject's parent/LAR.

7.2.4.10 Post Sleep Questionnaire

The PSQ is a 7-item questionnaire typically used to assess sleep quality with pharmacologic treatment. The questionnaire collects data on average time to sleep, sleep latency, frequency of interrupted sleep, duration of interrupted sleep, total sleep time and sleep quality over the last week. The PSQ will be completed by the parent/LAR with the subject and the responses will be reviewed by the clinician during the study visit. The PSQ will be completed at Baseline (Visit 2), and each visit through Visit 6/ET. The title, version, and date of the PSQ version used in this study are included in Appendix 3.

7.2.4.11 Columbia-Suicide Severity Rating Scale

The C-SSRS (Posner 2007) is a semi-structured interview that captures the occurrence, severity, and frequency of suicide-related thoughts and behaviors during the assessment period. The interview includes definitions and suggested questions to solicit the type of information needed to determine if a suicide-related thought or behavior occurred.

SHP465-309

07 September 2017

The C-SSRS contains 2 required items pertaining to suicidal ideation, 4 required items pertaining to suicidal behavior, and 1 required item pertaining to nonsuicidal self-injurious behavior. There are 8 additional suicidal ideation items and 2 additional suicidal behavior items which are completed in cases of positive responses for other items, as well as 2 items for completed suicide and suicide behavior present during the interview. Thus, there is a maximum of 19 items to be completed.

The C-SSRS must be performed by an individual who is medically responsible for the subject. All individuals performing this assessment must be preapproved by the sponsor or delegated vendor.

Two versions of the C-SSRS are used in this study:

- The "baseline" version will be administered at the screening visit (Visit 1) and will be completed for all subjects.
- The "since last visit" version will be completed for all subjects at all study visits after the screening visit (Visit 1).

The title, version, and date of the C-SSRS "Baseline" version and the C-SSRS "since last visit" version used in this study are included in Appendix 3.

7.2.4.12 Suitability of the Subject to Remain in the Study

At each visit (except for Visit 6/ET) starting with the baseline visit (Visit 2), the investigator will assess the subject's ability to continue in the study. The investigator or a medically qualified designee will review all available safety information (including sleep behavior, weight and BMI) and will evaluate for the presence of insomnia or decreased appetite potentially leading to weight loss. In cases where the subject has clinically significant decreases in appetite or insomnia, the investigator should intervene as necessary based on clinical judgment (eg, diet, behavioral interventions, sleep hygiene) and consider discontinuation of treatment if necessary. In any cases where a subject has clinically significant and persistent sleep difficulties (eg, the CSHQ score of ≥41 for 2 consecutive weeks since the beginning of treatment) or has had ≥7% weight loss the investigator must discuss the case with the medical monitor and assess whether it's in the best interest for the subject to remain in the study. The evaluation and decision should also be clearly documented in the subject's source notes.

As part of the assessment of the subject's suitability to remain in the study the investigator should also assess the subject's current potential for suicide, suicidal ideation, self-harm, or harm to others, as well as psychiatric disorders. The investigator should make this assessment by conducting a clinical interview with the subject and by reviewing of all other relevant sources available, including results of the C-SSRS. Any subject who has 1 or more positive responses must undergo further evaluation to ensure that they are not in any way at risk. As part of this assessment, if appropriate, the investigator should discuss risk factors for suicide with the subject. Where a subject has suffered an accidental injury, the investigator should ensure that this was a true accidental injury, rather than an episode of self-harming or a suicide attempt.

The investigator should pay particular attention to:

• Any 'yes' response to Items 2, 3, 4, or 5 on the C-SSRS or any suicidal behavior.

The subject's source notes should clearly document that the assessment of continued suitability including assessment of the subject's appetite, weight loss, insomnia and current potential risk of suicide, suicidal ideation, feelings of hopelessness, drug use, self-harm, or harm to others has taken place and should contain the decision on whether the subject is suitable to continue in the study.

7.2.5 Others

No clinical pharmacology, pharmacodynamic, pharmacogenomics, or health-related quality of life assessments will be performed.

7.2.6 Volume of Blood to be Drawn From Each Subject

Table 3: Volume of Blood to be Drawn From Each Subject

Assessment		Sample Volume (mL)	Number of Samples	Total Volume (mL)
Safety ^a	Biochemistry and Choriogonadotropin Beta (β-HCG) ^b	3	2	6
	Hematology ^a	2	2	4
Total mL				10

β-HCG= beta human chorionic gonadotropin

During this study, it is expected that approximately 10 mL of blood will be drawn from all subjects, regardless of sex.

Note: The amount of blood to be drawn for each assessment is an estimate. The amount of blood to be drawn may vary according to the instructions provided by the manufacturer or laboratory for an individual assessment; however, the total volume drawn over the course of the study should be approximately 10 mL. When more than 1 blood assessment is to be done at the time point/period, if they require the same type of tube, the assessments may be combined. If a catheter is used, the first 1 mL of blood from each sampling will be discarded.

^a Biochemistry and hematology clinical laboratory tests will be repeated at baseline if 32 days or longer have elapsed since the screening visit (Visit 1).

^bβ-HCG testing for females of childbearing potential only.

8 ADVERSE AND SERIOUS ADVERSE EVENTS ASSESSMENT

8.1 Definition of Adverse Events, Period of Observation, Recording of Adverse Events

An AE is any untoward medical occurrence in a clinical investigation subject administered a pharmaceutical product and that does not necessarily have a causal relationship with this treatment. An AE can therefore be any unfavorable and unintended sign (including an abnormal laboratory finding), symptom, or disease temporally associated with the use of a medicinal (investigational) product, whether or not related to the medicinal (investigational) product (ICH Guidance E2A 1995).

All AEs are collected from the time the informed consent is signed until the defined follow-up period stated in Section 7.1.3. This includes events occurring during the screening phase of the study, regardless of whether or not investigational product is administered. Where possible, a diagnosis rather than a list of symptoms should be recorded. If a diagnosis has not been made, then each symptom should be listed individually. All AEs should be captured on the appropriate AE pages in the CRF and in source documents. In addition to untoward AEs, unexpected benefits outside the investigational product indication should also be captured on the AE CRF.

All AEs must be followed to closure (the subject's health has returned to his/her baseline status or all variables have returned to normal), regardless of whether the subject is still participating in the study. Closure indicates that an outcome is reached, stabilization achieved (the investigator does not expect any further improvement or worsening of the event), or the event is otherwise explained. When appropriate, medical tests and examinations are performed so that resolution of event(s) can be documented.

8.1.1 Severity Categorization

The severity of AEs must be recorded during the course of the event including the start and stop dates for each change in severity. An event that changes in severity should be captured as a new event. Worsening of pretreatment events, after initiation of investigational product, must be recorded as new AEs (for example, if a subject experiences mild intermittent dyspepsia prior to dosing of investigational product, but the dyspepsia becomes severe and more frequent after first dose of investigational product has been administered, a new AE of severe dyspepsia [with the appropriate date of onset] is recorded on the appropriate CRF).

The medical assessment of severity is determined by using the following definitions:

Mild: A type of AE that is usually transient and may require only minimal treatment or

therapeutic intervention. The event does not generally interfere with usual

activities of daily living.

Moderate: A type of AE that is usually alleviated with specific therapeutic intervention. The

event interferes with usual activities of daily living, causing discomfort but poses

no significant or permanent risk of harm to the research subject.

Page 56

07 September 2017

Severe: A type of AE that interrupts usual activities of daily living, or significantly affects clinical status, or may require intensive therapeutic intervention.

8.1.2 **Relationship Categorization**

A physician/investigator must make the assessment of relationship to investigational product for each AE. The investigator should decide whether, in his or her medical judgment, there is a reasonable possibility that the event may have been caused by the investigational product. If there is no valid reason for suggesting a relationship, then the AE should be classified as "not related". Otherwise, if there is any valid reason, even if undetermined or untested, for suspecting a possible cause-and-effect relationship between the investigational product and the occurrence of the AE, then the AE should be considered "related". The causality assessment must be documented in the source document.

The following additional guidance may be helpful:

Term	Relationship Definition		
Related	The temporal relationship between the event and the administration of the investigational product is compelling and/or follows a known or suspected response pattern to that product, and the event cannot be explained by the subject's medical condition, other therapies, or accident.		
Not Related	The event can be readily explained by other factors such as the subject's underlying medical condition, concomitant therapy, or accident and no plausible temporal or biologic relationship exists between the investigational product and the event.		

8.1.3 **Outcome Categorization**

The outcome of AEs must be recorded during the course of the study on the CRF. Outcomes are as follows:

- Fatal
- Not Recovered/Not Resolved
- Recovered/Resolved
- Recovered/Resolved With Sequelae
- Recovering/Resolving
- Unknown

8.1.4 **Symptoms of the Disease Under Study**

Symptoms of the disease under study should not be classed as AEs as long as they are within the normal day-to-day fluctuation or expected progression of the disease and are part of the efficacy data to be collected in the study; however, significant worsening of the symptoms should be recorded as an AE.

8.1.5 **Clinical Laboratory and Other Safety Evaluations**

A change in the value of a clinical laboratory, vital sign, or ECG assessment can represent an AE if the change is clinically relevant or if, during treatment with the investigational product, a shift of a parameter is observed from a normal value to an abnormal value, or a further worsening of an already abnormal value. When evaluating such changes, the extent of deviation from the reference range, the duration until return to the reference range, either while continuing treatment or after the end of treatment with the investigational product, and the range of variation of the respective parameter within its reference range, must be taken into consideration.

If, at the end of the treatment phase, there are abnormal clinical laboratory, vital sign, or ECG values which were not present at the pretreatment value observed closest to the start of study treatment, further investigations should be performed until the values return to within the reference range or until a plausible explanation (eg. concomitant disease) is found for the abnormal values.

The investigator should decide, based on the above criteria and the clinical condition of a subject, whether a change in a clinical laboratory, vital sign, or ECG parameter is clinically significant and therefore represents an AE.

8.1.6 **Pregnancy**

All pregnancies are to be reported from the time informed consent is signed until the defined follow-up period stated in Section 7.1.3.

Any report of pregnancy for any female study participant must be reported within 24 hours to the Shire Pharmacovigilance Department using the Shire Investigational and Marketed Products Pregnancy Report Form. A copy of the Shire Investigational and Marketed Products Pregnancy Report Form (and any applicable follow-up reports) must also be sent to the CRO/Shire Medical Monitor using the details specified in the emergency contact information section of the protocol. The pregnant female study participant must be withdrawn from the study.

Every effort should be made to gather information regarding the pregnancy outcome and condition of the infant. It is the responsibility of the investigator to obtain this information within 30 calendar days after the initial notification and approximately 30 calendar days post partum.

Pregnancy complications such as spontaneous abortion/miscarriage or congenital abnormality are considered SAEs and must be reported using the Shire Clinical Trial Serious Adverse Event Form. Note: An elective abortion is not considered an SAE.

In addition to the above, if the investigator determines that the pregnancy meets serious criteria, it must be reported as an SAE using the Shire Clinical Trial Serious Adverse Event Form as well as the Shire Investigational and Marketed Products Pregnancy Report Form. The test date of the first positive serum/urine β-HCG test or ultrasound result will determine the pregnancy onset date.

SHP465-309

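### Protocol 8.1.2 gives two conflicting causality rules: an adverse event with a plausible drug link plus another explanation, or with only a weak link, is 'related' by the text but fits neither row of the guidance table

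*Protocol*

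**What the plan says.** Protocol 8.1.2 (Relationship Categorization) asks the physician or investigator for a two-way judgement on each AE.

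- **Text, negative side:** "If there is no valid reason for suggesting a relationship, then the AE should be classified as" not related.
- **Text, positive side:** in every other case the AE is related, that is, "if there is any valid reason, even if undetermined or untested, for suspecting a possible cause-and-effect relationship".

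A two-row table follows. It is introduced with "The following additional guidance may be helpful", and its second column is labelled as the definition of the relationship.

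- **'Related' row:** the timing is compelling and/or the event "follows a known or suspected response pattern to that product". A second condition must hold as well: "and the event cannot be explained by the subject's medical condition, other therapies, or accident".
- **'Not Related' row:** two conditions must both hold. The first is a ready alternative cause, for example an existing illness or another treatment. The second is that "no plausible temporal or biologic relationship exists between the investigational product and the event".

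The classification is used in several places. SAP 12.1 reports related TEAEs in the overall summary, tabulates TEAEs by system organ class, preferred term and relationship, and lists the related ones. SAP 19.9 counts a TEAE with a missing relationship as related in incidence summaries. Protocol 8.2.7 has authorities, central IRBs and active sites notified of SAEs that are both related and unexpected. Protocol 8.2.4 asks for reports of SAEs found after the study only if they are considered related.

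**The concern.** The text sets a low bar: a valid suspicion is enough, and other causes need not be ruled out. The table reverses this for 'Related', because its second condition is joined by 'and' and requires that nothing else can explain the event. The 'Not Related' row is also a conjunction, so failing one row does not place an event in the other.

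The cases caught in between are foreseeable. Protocol 1.2.1 names insomnia, decreased appetite, decreased weight, increased heart rate and anxiety as product effects. Protocol 5.2.1 permits stable bronchodilator inhalers, among other treatments. It is my inference that some children will have such an event together with a concurrent treatment or condition that could also account for it.

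Neither document says that the text prevails, and the SAP names no governing rule for its related-TEAE tables. One investigator may code by the text and another by the table. With about 60 children at about 45 sites (60/45 = 1.3 per site on average), such differences in reading could not be separated from differences between children.

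**Working it through.** The documents give no figure on this point, so the first check is logical.

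**Step 1: put every case through both rules.** I take a plausible temporal or biologic link to be a valid reason in the sense of the text. A link is strong if the timing is compelling or the pattern is known or suspected.

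| Link to product | Other explanation? | Text | Table |
|---|---|---|---|
| Strong | No | Related | Related |
| Strong | Yes | Related | Neither row |
| Plausible, not strong | Yes | Related | Neither row |
| Plausible, not strong | No | Related | Neither row |
| Not plausible | Yes | Not related | Not Related |
| Not plausible | No | Not related | Neither row |

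The text classifies all six cases. The table classifies two, and these are the only two in which it agrees with the text.

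**Step 2: direction.** In the three cases that are related by the text but meet neither row, an investigator who sees the 'Related' test fail and enters 'Not Related' lowers the related count. One who defaults to 'Related' agrees with the text there, but departs from it in the last case. A field left blank is counted as related under SAP 19.9. An event actively coded 'Not Related' is not recovered by that rule.

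**Step 3: size per child.** About 60 children randomized 1:1 gives 30 per arm, so one child is 1/30 = 3.3 percentage points. A child leaves the overall related count only if all of that child's related TEAEs are recoded.

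**Step 4: illustration with assumed inputs.** Let g be the share of children with a text-related TEAE who lose that status because gap events are coded 'Not Related'. Then

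rate under table = rate under text × (1 − g).

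| Text rate (assumed) | g = 0 | g = 0.25 | g = 0.5 | g = 0.75 |
|---|---|---|---|---|
| 12/30 = 40% | 40% | 30% | 20% | 10% |
| 6/30 = 20% | 20% | 15% | 10% | 5% |

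The documents give neither the text rate nor g. The shift can be zero, and the table shows a range, not a forecast.

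**The case against.** The best reply is that the documents already rank the two rules: the text is directive and covers every AE, while the table is only offered as possibly helpful. An investigator who gives the text precedence has no unclassifiable event. That is fair, but it does not remove the conflict. The table is labelled as a definition, it contradicts the rule that it is meant to explain, and nothing states which prevails.

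Other parts of the reply stand and limit the point:

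- A reader might infer that common stimulant effects in general fit neither category. They do not fall in the gap as a class: insomnia or decreased appetite with no competing cause follows a known pattern and meets the table's 'Related' row. Protocol 4.2 also narrows the competing causes by excluding primary sleep disorders, eating disorders, comorbid psychiatric disorders and CNS-active medication. Section 8.1.4 keeps ordinary fluctuation of ADHD symptoms out of the AE data.
- A reader might infer that an SAE could be kept from the sponsor. Under 8.2.2 and 8.2.4, SAEs up to the end of follow-up go to the sponsor's pharmacovigilance department and the medical monitor within 24 hours, whatever their relationship. Section 8.2.7 also makes the investigator responsible for local notification of all SAEs at the site, as required.
- Insomnia, weight decrease and decreased appetite have their own displays in SAP 12.1.1, by arm and by week, and these do not depend on causality.
- The related-TEAE tables are descriptive, and assessment is double-blind with the same rule in both arms. Blinding guards against deliberate differential coding, but it does not restore an absolute rate from which gap events have dropped out.
- The CRF is not among the documents, so nothing can be said about the choices it offers.

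**Conclusion.** The conflict is real and lies in the wording of Protocol 8.1.2. It concerns AEs with a plausible product link and a competing explanation, and AEs whose link is plausible but neither compelling in timing nor part of a known or suspected pattern. These are related by the text and meet neither table row.

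The consequence is limited. Related-TEAE rates can be lowered by 3.3 points per reclassified child, assuming 30 per arm. The number reclassified cannot be obtained from the documents, so any particular total shift, such as 10 points for three children, is an illustration only. The coding also bears on which SAEs count as related for notification under 8.2.7 and on the reporting of SAEs found after the study under 8.2.4. It does not bear on efficacy, total TEAE rates, or SAE reporting to the sponsor during the study.

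I rate this as a low-priority clarification, worth making because it costs almost nothing.

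**What to change.** In Protocol 8.1.2, or in a clarification note to sites:

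1. State that the text governs and that the table only illustrates it.
2. In the 'Related' row, delete the condition that nothing else can explain the event, and let the row cover any reasonable possibility of a causal link.
3. Define 'Not Related' as no valid reason for suspicion, that is, no plausible temporal or biologic relationship. A ready alternative explanation may support that judgement but should not be required.

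Step 3 matters. If the present 'Not Related' row were kept and everything else called related, an event with no plausible link and no ready alternative would become related, against the text. With all three steps the rows are exhaustive and agree with the text in all six cases above.

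The SAP should name the same rule in 12.1. If coding is complete but treatment is still blinded, TEAEs coded 'Not Related' could be queried against it.

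The cost is a short clarification and a site reminder. The downside is that the related-TEAE rate may be slightly higher in both arms.
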